## Plan for Data Quality Control Procedures

The PI and the project manager will review all data collection forms and surveys on an ongoing basis for data completeness and accuracy as well as protocol compliance. Any ambiguity in the response to a question will be brought to the attention of the Project Manager for clarification. If the Project Manager is unsure how to resolve the issue, the matter will be brought to the attention of the Principal Investigator. The Project Manager will maintain a log so that future occurrences of problems will be handled in the same manner. Further, these issues will be discussed during project meetings to ensure that data resolution is handled consistently.

The data entry system (RedCap) requires a login identification and password in order to gain access to the data. Where appropriate, validation and range rules are applied to the actual entry field. Data found to be inconsistent after the verification has been run will be compared to original questionnaires and recorded values to resolve any discrepancies.

## Data Safety Monitoring Responsibilities

The entire team for this project will meet at least monthly in the first year in order to coordinate planning of the study and oversee recruitment efforts. Staff, graduate assistants, and the PI will meet weekly. In addition, weekly individual meetings with the PI and project coordinator will occur to ensure recruitment efforts are yielding our target goals and weekly meetings with the PI and the nutrition interventionist will occur in order to ensure intervention content is being developed/collected in a timely manner. The project coordinator will oversee the monthly reports to the DSMB that detail recruitment efforts and enrollment demographics. Sub-committees for each aim will also be formed. All sub-committees will be led by PI [name]. Sub-committees for Aim 1 will include Drs. [name] and [name]; Aim 2 will include Drs. [name] and [name]. Progress reports, including participant recruitment, retention/attrition, and adverse events (AEs), will be provided to the DSMB semi-annually. An Annual Report will be compiled and will include a list and summary of AEs, whether AE rates are consistent with pre-study assumptions, reason for

dropouts from the study, whether all participants met entry criteria, whether continuation of the study is justified on the basis that additional data are needed to accomplish the stated aims of the study, and conditions whereby the study might be terminated prematurely.

The Annual Report will be sent to the DSMB and will be forwarded to the USC IRB and NIH. The USC IRB will review progress of this study on an annual basis. The PI will also send copies of signed recommendations and comments from the DSMB to the NIH Program Officer within 1 month of each monitoring review.

## Statistical Design and Power

I. The below statistical plan justifies the proposed sample size based on appropriate study assumptions, as well as our plans for evaluation of the primary outcomes by race/ethnicity and sex, including all relevant data that assess whether the trial includes adequate numbers for valid analyses of subgroups. Below we also justify the adequacy of power to analyze subgroups of participants:

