## **Secondary Aims**

Examine usage patterns over time (e.g., do points sustain engagement and promote weight loss maintenance?), potential mediators (e.g., engagement/self-monitoring) and moderators (demographic factors such as sex, race, age), the usability and acceptability of the interventions and the association of social support provision/receipt and psychosocial factors (e.g., motivation, enjoyment) with weight loss. Create and test predictive models that can be applied to future grant applications.

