## Randomization Procedure

Participants were randomized to a gamified (*mLife+points*) or non-gamified (*mLife*) version of the *mLife* mobile weight loss intervention where provision of social support was incentivized by providing points for engaging in social support activities (for the *mLife+points* group) or not receiving points for social support activities (*mLife* group).

Participants are randomly assigned once 50% of the baseline assessments are completed (either the baseline survey or the three dietary recalls). A computerized blocks system, stratified by race (Black, Other) and sex, is used to ensure equal distribution among groups within each cohort. [name] generates a random list of two groups (0s = Standard, 1s = *mLife*) in blocks of 10 or 4. Separate blocks are created for women and men, as well as white and non-white participants, this results in 15 blocks of 10 for non-white women, 30 blocks of 10 for white women, 3 blocks of 5 for non-white men, and 5 blocks of 4 for white men.

As participants complete 50% of the assessment, a blind staff member uses the demographic data report from RedCap to identify each participant by gender and race and add the participant's ID number to the next available spot on the blocks. The group allocation will then be recorded in the RedCap project under the randomization form (randomization event). Participants will not be informed of their group assignment but will be provided with their choice of meeting times and days for the training session. On the day of randomization, participants will be contacted and asked to select the time and date they plan to attend. The group allocation will be revealed at the first group meeting, after all baseline assessments have been completed. Since the training sessions are scheduled by group, the randomization process must occur before inviting participants to the training meeting.

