### ***Aims 1 and 2***

We are powering our study to detect differences in weight loss at one year between those randomized to mLife+points and mLife groups (Aim 1) and differences in social support provision and receipt at one year between groups (Aim 2). For Aim 1 power, we used an F-test on the interaction between time (two levels) and treatment arm (two levels) in a two-way ANOVA with repeated measurements. We assumed **conservatively** a small effect size (Cohen's  $d = 0.1$ ).

Moreover, we used our NETworks pilot work, which collected weight loss outcomes at one year, to determine the intra-cluster correlation (ICC) which is the correlation of weight between times within individuals. The pilot study estimate of the ICC was 0.9 but we judged that this estimate may be too optimistic and lead to an inadequately low sample size (see Table 5). Therefore, we used a more **conservative** ICC = 0.7. In summary, we calculated that to achieve 95% power (alpha = 0.05) for Aim 1 assuming a small effect size (Cohen's  $d = 0.1$ ) and ICC equal to 0.7, we need a sample size equal to 200. Further, we assumed an attrition rate of 15-20% and increased the sample size to 240. Thus, we aim to recruit a total of 240 participants (~120 per cohort), with the initial randomization assigning 120 to mLife+points and 120 to mLife. This sample size will also give us abundant power for the study in Aim 2. Based on our Social POD pilot work, we are powering Aim 2 from both differences in overall app usage (Social POD  $50.7 \pm 25.0$  days and standard  $34.4 \pm 25.8$  days out of a possible 84 days) and points earned (representing social support provision). Social POD pilot participants earned a mean of  $202 \pm 105$  points/participant. We are assuming a difference of 50 points between groups with a SD of 105. Therefore, with the sample size chosen for Aim 1, our

power for Aim 2 will be 99% for app usage and 95% for points earned.

The sample size for our study has been chosen to ensure sufficient statistical power to detect differences in weight loss at one year after baseline between those randomized to mLife+points and mLife groups (Aim 1) and differences in social support provision and receipt and at one year between groups (Aim 2).

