## V. Consideration of relevant biological variables

Of primary interest in the present study will be examining differences in outcomes by sex and age. Previous research has demonstrated that men lose more weight than women in behavioral weight loss interventions, but there is no indication that different weight loss strategies should be used. There is evidence that men may interact with technology, including health-related mobile technology, differently than women. For example, a study examining gender differences in usage of a physical activity app found that enjoyment and goal-setting were more important for women than men but that men more often shared their results and used the live tracking function in the app. Other research has found that men feel that mobile phone usage is more appropriate across a variety of social situations than women. In addition, those under 50 (and particularly those under 30) tend to have higher rates of smartphone ownership than those over 50. Based on these findings, we aim to conduct sub-analyses examining the impact of sex and age on social support provision and receipt and weight loss. We have been successful recruiting both men and AA participants in our previous studies and being situated in South Carolina and housing this work within the Prevention Research Center (where the current main research project is among AA churches in SC) will ensure we can consider both of these relevant biological variables. Our models will also control for other factors that could impact outcomes, including age, BMI, SES, baseline lab values, and medication use.

**A. Below details our approach to data management and validation, including our data management system, methods of data entry and cleaning, and event tracking and logistics**  
 [name], Project Manager, and [name], study PI, will develop and maintain the computerized data management system for this study. Use of the data management system will be restricted to only those persons having access authority.

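### The plan says subgroup power is adequate and justified below, but no justification appears in the available text, and on the plan's own weight-outcome inputs no split of 200 participants supports the claim for both subgroups or for an interaction no larger than the overall effect

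*Combined protocol and SAP*

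**What the plan says.** The opening paragraph of Statistical Design and Power says the plan will cover "our plans for evaluation of the primary outcomes by race/ethnicity and sex, including all relevant data that assess whether the trial includes adequate numbers", meaning enough participants to analyse subgroups validly. It then adds: "Below we also justify the adequacy of power to analyze subgroups of participants". The factors named there are race/ethnicity and sex.

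The text that follows (Aims 1 and 2; Sample size according to F-test) gives power for whole-sample contrasts only. For Aim 1, "we used an F-test on the interaction between time (two levels) and treatment arm (two levels") in a repeated-measures ANOVA, "to achieve 95% power (alpha = 0.05) for Aim 1", with an effect size of 0.1 labelled Cohen's d and an ICC of 0.7. That gives 200, raised to 240 for 15-20% attrition. For Aim 2, power is 99% for app usage and 95% for points earned.

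The Aim 1 model in the Analysis Plan contains time, treatment, their interaction and covariates. It has no treatment-by-subgroup term.

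Analysis Plan section V then says: "Of primary interest in the present study will be examining differences in outcomes by sex and age", and "we aim to conduct sub-analyses examining the impact of sex and age on social support provision and receipt and weight loss". It cites past success in recruiting men and African American participants, but gives no expected numbers. The Secondary Aims list "moderators (demographic factors such as sex, race, age") for study. The set of factors therefore differs between the three places.

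**The concern.** The plan states a design property, adequate subgroup power, and says the support for it follows. If the support is missing and the property does not hold on the plan's own inputs, two errors become likely at reporting. A non-significant subgroup result could be read, with the plan's assurance behind it, as evidence that the effect does not differ by sex, race or age. And if the subgroups are tested separately, one may reach significance and the other not by chance, and the contrast may then be reported as a real difference. The plan does not commit to separate tests, but it specifies no interaction test either, so it leaves this open.

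**Working it through.** **Inputs.** From Aims 1 and 2: 200 evaluable, 1:1 allocation, alpha 0.05 (a 1-df F-test, hence two-sided), correlation ρ = 0.7, effect 0.1. Not in the documents, so assumed here: the subgroup split and the size of the interaction.

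**Step 1: reproduce the plan's 200.** For the time-by-arm F-test with two time points, λ = f²·N·2/(1−ρ), df = (1, N−2). With f = 0.1, ρ = 0.7 and N = 200, λ = 0.01 × 200 × 2/0.3 = 13.33 and power is 95.3%. The smallest N for 95% is 198, so 200 reproduces.

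Read literally as d = 0.1, it does not reproduce. A difference of 0.1 SD of weight needs 1,560 per arm (15% power at 200), and 0.1 SD of change needs 2,599 per arm (11% at 200). The check therefore uses f.

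**Step 2: express the effect in SDs of change.** f = 0.1 corresponds to a difference in change of 0.4 SD of weight. The SD of change is √(2 × 0.3) = 0.775, so the effect is 0.4/0.775 = 0.516 SD of change.

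**Step 3: power within a subgroup of size n.** The noncentrality is 0.516 × √n/2, with n−2 df.

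| n in subgroup | Power |
|---|---|
| 35 | 32% (31% with 17 per arm) |
| 100 | 72.5% |
| 120 | 80% |
| 165 | 91% |

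Reaching 80% takes about 120, so both subgroups reach it only if 2 × 120 = 240 are evaluable. With 200, no split does this.

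**Step 4: power for a treatment-by-subgroup interaction.** In SDs of change, SE = 2·√(1/n₁ + 1/n₂), with N−4 df. For 100 against 100, SE = 2 × √0.02 = 0.283. For 35 against 165, SE = 0.372. The SE is smallest at an equal split, so that is the best case.

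| Interaction relative to overall effect | 100 v 100 | 35 v 165 |
|---|---|---|
| half (0.258 SD) | 15% | 11% |
| equal (0.516 SD) | 44.3% | 28% |
| 1.5 times (0.775 SD) | 78% | 54% |
| twice (1.033 SD) | 95% | 79% |

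The column with 35 men is an assumption. The Randomization Procedure prepares "3 blocks of 5 for non-white men, and 5 blocks of 4 for white men", that is 15 + 20 = 35 male slots out of 150 + 300 + 15 + 20 = 485. With 485 slots for 240 participants, this is list capacity and not a recruitment target.

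**Step 5: sensitivity at 50:50, interaction equal to the overall effect.**
- Evaluable N: 42.9% at 192, 45.0% at 204, 51.3% if all 240 are retained.
- ρ = 0.9 (the pilot estimate), same f: effect 0.4/√0.2 = 0.894 SD of change; power 88% for the full-size interaction, 35% for half of it, and 67% with 35 men.
- 0.1 taken literally as d: about 7%.

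**Step 6: detectable interaction at 80% power.** 2.80 × SE is 2.80 × 0.283 = 0.79 SD of change at 50:50, or 0.79/0.516 = 1.5 times the overall effect. With 35 men of 200 it is 2.80 × 0.372 = 1.04 SD, or 2.0 times.

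At 50:50, about 476 evaluable participants would be needed for 80% power to detect an interaction equal to the overall effect.

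**The case against.** The strongest reply is that the plan promises power to analyse subgroups without naming an interaction test or a threshold. On that wording, a large subgroup is adequately powered on its own: 80% at 120 and 91% at 165. This stands. A reader might infer that the claim fails for every subgroup under every split, and the plan's inputs do not support that. They show that the two subgroups cannot both reach 80% with 200 evaluable, and that an interaction no larger than the overall effect cannot reach it either.

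The 44% is also conditional. It assumes an interaction as large as the whole treatment effect, takes 0.1 as f where the plan writes d, and uses ρ = 0.7. An interaction twice as large gives 95%, and ρ = 0.9 gives 88% at 50:50. These conditions have to be stated with the figure. They do not restore the claim: the plan names no interaction size, it set 0.9 aside as possibly too optimistic, and the literal d reading lowers power to about 7%.

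A reader might also take the male block slots to mean that at most 35 men are expected. The documents give no sex split, so the figures for 35 men are illustrative.

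The moderators sit under Secondary Aims, so the primary test is not at risk. This also stands, although section V describes sex and age differences as of primary interest.

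Finally, absence is hard to prove. A cited Table 5 is not shown, and the Analysis Plan headings run from I to III. The table is cited for the ICC and sample size, and neither gap is evidence of a subgroup calculation. The accurate statement is that none appears in the available text.

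**Conclusion.** The concern holds in this form: wrong as written. No calculation is needed to see that the promised justification does not appear in the available text. On the plan's weight-outcome inputs (200 evaluable, ρ = 0.7, two-sided 0.05 without multiplicity adjustment, 0.1 read as f), the best-case split falls short of 80% within each half and well short for an interaction the size of the overall effect. The social support outcomes in the section V sub-analyses have their own assumptions and were not assessed for subgroup power. The primary comparison is unaffected. What needs correcting is a stated design property that the design inputs do not support.

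**What to change.** - In Statistical Design and Power, delete the statement that subgroup power is adequate and justified.
- State one list of subgroup factors, the same in Secondary Aims, Statistical Design and Power, and Analysis Plan section V, and label the sex, race and age analyses exploratory.
- Test each factor by adding a treatment-by-subgroup interaction to the outcome model (in the Aim 1 repeated-measures model, the time-by-treatment-by-subgroup term), and report the estimate with its 95% confidence interval.
- Report the detectable interaction at 80% power with its assumptions: about 0.8 SD of change at 50:50, and about 1.0 SD if 35 of 200 are men. Update it once the actual subgroup sizes are known.
- State that no subgroup contrast will be drawn from separate within-subgroup p-values.

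The cost is a few sentences and an interaction term in analyses already intended. No new data or participants are needed.

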### ***Aims 1 and 2***

We are powering our study to detect differences in weight loss at one year between those randomized to mLife+points and mLife groups (Aim 1) and differences in social support provision and receipt at one year between groups (Aim 2). For Aim 1 power, we used an F-test on the interaction between time (two levels) and treatment arm (two levels) in a two-way ANOVA with repeated measurements. We assumed **conservatively** a small effect size (Cohen's  $d = 0.1$ ).

Moreover, we used our NETworks pilot work, which collected weight loss outcomes at one year, to determine the intra-cluster correlation (ICC) which is the correlation of weight between times within individuals. The pilot study estimate of the ICC was 0.9 but we judged that this estimate may be too optimistic and lead to an inadequately low sample size (see Table 5). Therefore, we used a more **conservative** ICC = 0.7. In summary, we calculated that to achieve 95% power (alpha = 0.05) for Aim 1 assuming a small effect size (Cohen's  $d = 0.1$ ) and ICC equal to 0.7, we need a sample size equal to 200. Further, we assumed an attrition rate of 15-20% and increased the sample size to 240. Thus, we aim to recruit a total of 240 participants (~120 per cohort), with the initial randomization assigning 120 to mLife+points and 120 to mLife. This sample size will also give us abundant power for the study in Aim 2. Based on our Social POD pilot work, we are powering Aim 2 from both differences in overall app usage (Social POD  $50.7 \pm 25.0$  days and standard  $34.4 \pm 25.8$  days out of a possible 84 days) and points earned (representing social support provision). Social POD pilot participants earned a mean of  $202 \pm 105$  points/participant. We are assuming a difference of 50 points between groups with a SD of 105. Therefore, with the sample size chosen for Aim 1, our

power for Aim 2 will be 99% for app usage and 95% for points earned.

The sample size for our study has been chosen to ensure sufficient statistical power to detect differences in weight loss at one year after baseline between those randomized to mLife+points and mLife groups (Aim 1) and differences in social support provision and receipt and at one year between groups (Aim 2).

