### **Sample size according to F-test**

Because our main outcomes will be measured at 12 months, we are using pilot work that collected weight loss outcomes at one year. Based on our pilot data (NETworks trial as this provides 12-month outcomes for weight), as well as several other one-year mHealth intervention studies, we calculated the sample size necessary to achieve 95% power (alpha = 0.05) for Aim 1 assuming a small effect size (Cohen's  $d = 0.1$ ) and an intra-cluster correlation (ICC) equal to 0.7. The sample size estimate was 200. For this calculation, we used an F-test on the interaction between time (two levels) and treatment arm (two levels) in a two-way ANOVA with repeated measurements (RM-ANOVA). We used a more conservative value of the ICC as compared to the actual estimate from the NETworks trial data (ICC = 0.9), as the latter would have resulted in a much smaller sample size (for a larger ICC, the residual sum of squares decreases, therefore precision increases and sample size decreases. The opposite is true when the test is strictly between subjects). Further, we assumed an attrition rate between 15 and 20%, and increased the sample size to 240. Thus, we aim to recruit a total of 240 participants (~120 per cohort), with the initial randomization assigning 120 to SocialPOD+points and 120 to SocialPOD-points.

Based on pilot study for overall app usage (Social POD  $50.7 \pm 25.0$  days and standard  $34.4 \pm 25.8$  days out of a possible 84 days) and points earned (mean of  $202 \pm 105$  points/participant with estimated 50 point difference between groups), our power for Aim 2 will be 99% for app usage and 95% for points earned based on our sample size from Aim 1.

We plan to use a random-effects (RE) model which is mathematically equivalent to repeated-measures-ANOVA. However, in the presence of loss to follow-up, RE models can handle responses that are missing at random. RE models can be adjusted for additional covariates if needed (though the randomization procedure should make this unnecessary). RE models provide additional information about the variance of the random effects which is valuable for understanding heterogeneity of responses and assessing the intra-cluster correlation (ICC).

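### The Aim 1 sample size of 200 follows from Cohen's f = 0.1, not the stated Cohen's d = 0.1; the trial is powered for about half an SD of weight change, not for a conservatively small effect

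*Combined protocol and SAP*

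**What the plan says.** The Aim 1 power statement appears twice under Statistical Design and Power, in Aims 1 and 2 and in Sample size according to F-test. Both give the same inputs: Cohen's d = 0.1, within-person correlation (called ICC) 0.7, alpha 0.05 and 95% power.

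- On the test: "we used an F-test on the interaction between time (two levels) and treatment arm (two levels) in a two-way ANOVA with repeated measurements".
- On the result: "we calculated that to achieve 95% power (alpha = 0.05) for Aim 1 assuming a small effect size" and "and ICC equal to 0.7, we need a sample size equal to 200". The second section repeats it: "The sample size estimate was 200".
- On the correlation: "The pilot study estimate of the ICC was 0.9", and 0.7 was chosen as the more cautious value.

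The Aims 1 and 2 section presents the effect size itself as a conservative assumption. The 200 is then raised to 240 for 15–20% attrition. Neither section mentions Cohen's f, an SD of weight or of weight change, or a target difference in kg. The Analysis Plan (part III) tests Aim 1 with the same interaction, baseline against 12 months, at the 0.05 level.

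**The concern.** A standardised difference of 0.1 is very small, and detecting it with 95% power normally takes thousands of participants. Within-person correlation helps, but at 0.7 the variance of change is still 2(1 − 0.7) = 0.6 of the variance of weight. That is far too small a gain to bring the requirement down to 200. The likely explanation is that 0.1 was entered as f and reported as d.

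The two are not interchangeable here. The stated power is the basis for enrolling 240 and part of how a null result would be read. A reader who believes the trial had 95% power at d = 0.1 would take a null result as strong evidence that points have almost no effect on weight.

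**Working it through.** **Inputs.** Two arms, 1:1; m = 2 time points; ρ = 0.7; alpha 0.05; target power 95%; stated N = 200 (both power sections). The F-test is non-directional and has 1 and N − 2 degrees of freedom, so it is equivalent to a two-sided t-test on change.

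**Formula.** For the interaction, the noncentrality is λ = f² × N × m/(1 − ρ).

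**Reproducing the plan's figure.** With f = 0.1 and N = 200, λ = 0.01 × 200 × 2/0.3 = 13.33 and power is 95.3%. The smallest even N reaching 95% is 198. This matches the stated 200.

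**What f = 0.1 means.** Let δ be the between-arm difference in change and σ the SD of weight. The interaction effect in each of the four cells is ±δ/4, so f = δ/(4σ).

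- On the SD of weight: δ = 4 × 0.1 = 0.40 σ.
- On the SD of change, which is σ√(2(1 − 0.7)) = 0.775 σ: 0.40/0.775 = 0.52.

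Cross-check: a two-sample t-test on change with 100 per arm and a standardised difference of 0.516 has λ = 0.516² × 200/4 = 13.3 and power 95.3%, the same result.

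**Taking d = 0.1 at its word.** The plan does not say which SD d refers to, so three readings were tried.

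| Reading of 0.1 | λ at N = 200 | Power at 200 | Power at 240 | Total N for 95% |
|---|---|---|---|---|
| Cohen's f | 13.33 | 95.3% | 97.9% | 198 |
| d, converted as f = d/2 = 0.05 | 3.33 | 44% | 51% | 782 |
| d on SD of weight (f = 0.025) | 0.83 | 15% | 17% | 3,122 |
| d on SD of change | 0.1² × 200/4 = 0.50 | 11% | 12% | 5,200 |

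Other variants do not rescue d = 0.1:

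- One-sided testing needs about 652, 2,598 or 4,330 for the three d readings in order.
- Baseline-adjusted analysis (ANCOVA), with d on the SD of weight, needs about 2,652.
- The pilot correlation of 0.9 needs 262 (f = 0.05) or about 1,040 (d on SD of weight). It makes no difference when d is on the SD of change.

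For comparison, d = 0.2 on weight change has λ = 0.2² × 200/4 = 2.0 and 29% power at N = 200.

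**In kg (illustrative).** The plan gives no 12-month SD. The synopsis reports 3-month pilot losses of 5.3 kg (n = 26) and 2.2 kg (n = 25), p = 0.02. If that p-value came from an unadjusted t-test on all 51, the standard error is 3.1/2.405 = 1.289 kg. The SD of change is then 1.289/√(1/26 + 1/25) = 4.6 kg. The difference with 95% power at N = 200 is 0.516 × SD of change:

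| Assumed SD of change | Difference |
|---|---|
| 4.6 kg (back-calculated, 3 months) | 2.4 kg |
| 6 kg | 3.1 kg |
| 8 kg | 4.1 kg |

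**The case against.** The strongest defence is that this is a mislabelled symbol. With f in place of d, every other stated input reproduces the sample size, and 0.1 is conventionally called small on the f scale. That probably explains the wording, but it does not make the statement true. The plan writes d twice, and at this correlation the difference in weight change is not small.

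The choice of correlation was indeed cautious: f = 0.1 with 0.9 would need only 68. That supports the ICC assumption, not the effect size.

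Calling the powered effect medium depends on scale. It fits 0.52 SD of change; 0.40 SD of weight lies between small and medium. Both should be reported.

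The kg figures are the softest part. All three SDs of change are assumptions, and 4.6 kg also rests on an assumed test and a 3-month outcome. At ρ = 0.7 they imply SDs of weight of only 5.9, 7.7 and 10.3 kg, which look low for a BMI range of 25–49.9. Starting instead from an assumed SD of weight of 15–20 kg, f = 0.1 is 6–8 kg. The two routes differ because 0.52 SD of change holds at N = 200 whatever the correlation, whereas 0.40 SD of weight holds only at 0.7. The kg value therefore needs a stated SD of change.

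A null result should be read mainly from its confidence interval. Table 5, cited in the power text, was not available to check. Neither point alters the arithmetic.

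**Conclusion.** The concern holds. The stated inputs do not give 200: at d = 0.1, power with 200 participants is 11–44% rather than 95%, and no reading of d tried brings the requirement to 200. The trial as sized has 95% power for a between-arm difference of about 0.52 SD of weight change, equal to 0.40 SD of weight if the correlation is 0.7. This assumes equal arms, a two-sided 0.05 test and 200 analysed participants. Analysing all 240 would raise power at d = 0.1 only to 12–51%.

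This is an error in the power claim, not proof that the trial is too small. The design may still suit an effect like the pilot's, but the plan does not make that case because it gives no SD or kg target.

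**What to change.** In both power sections:

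1. Replace Cohen's d = 0.1 with Cohen's f = 0.1.
2. Add that this is a between-arm difference in 12-month weight change of 0.40 SD of weight, or 0.52 SD of change, at correlation 0.7.
3. Give that difference in kg, naming the SD of change used and its source.
4. Remove the descriptions of the effect size as conservative and small. The remark that an ICC of 0.7 is conservative can stay.
5. State that power at N = 200 for d = 0.1 to 0.2 on weight change is about 11% to 29%.

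No change to N, the test or the analysis is needed. The cost is a wording amendment and a less favourable power statement.
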